The post-baseline study day at which the pre-defined responder status occurs will be used in the analysis of number of days to responder status analyses. If a subject never reaches the pre-defined responder status then the number of days will be censored at Day 28 or the day of the last particular efficacy assessment, whichever is earliest. Number of days to responder status will be analyzed by the Cox proportional hazards model with the baseline mean NRS score pain intensity score of interest as a covariate^[4]. The adjusted hazard ratio, 95% CI, and a p-value will be provided from the model

for each NYX-2925 treatment groups versus Placebo. The n (%) of subjects who are considered a responder as well as the n (%) of censored observations will be presented for each treatment group. Here is the SAS® Code:

PROC PHREG DATA=ADAM:

CLASS TRTP;

MODEL AVAL*CNSR(1) = TRTP BASEPAIN / RISKLIMITS=WALD;

RUN;

Additionally, the Kaplan-Meier method will be analyzed for the probability plots only. The same censoring technique will be used as stated in the Cox proportional hazards model. Here is the SAS® Code:

PROC LIFETEST DATA=ADAM CONFTYPE=LINEAR METHOD=KM ALPHA=0.05;

TIME AVAL*CNSR(1);

STRATA TRTP;

RUN;

The specific number of days to responder statuses calculated will be described in Section 9.3.3 and the number of days to sustained pain reduction in Section 9.3.4 of the SAP.

5.3.5.5Frequency Distribution Tests

Frequency distributions that have two responses (i.e. yes/no) and compare two different treatment groups (i.e. active versus placebo) may use a chi-square test for reporting a p-value. This is referred to as a 2x2 table. If the expected cells counts for any of the 2x2 tables are not \geq 5, then Fisher's exact test will be used instead. Each p-value using Fisher's exact test will be denoted in any summary table.

Odds ratio and relative risk estimates will be provided when chi-square or Fisher's exact test p-values are reported in summary tables^[4]. Both the odds ratio and relative risk estimates will be based on the "yes" responders of the active treatment as the numerator compared to the placebo treatments as the denominator in these estimates. 95% confidence intervals will also be provided for both odds ratio and relative risk estimates. Here is the SAS® code:

PROC FREQ DATA=ADAM;

WEIGHT COUNT;

/* where # is based on the type of responder criterion in CRIT#FLN */

TABLES TRTP*CRIT#FLN / FISHER CHISQ RELRISK;

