9.3.2 Responder Status Endpoints

Different efficacy responder statuses will be defined based on the following methods [4, 10]:

- Responder at $\geq 30\%$ Pain Reduction:
 - Subjects achieving ≥30% pain reduction on the mean NRS score assessing average pain intensity in the past 24 hours from baseline to Week 4 analysis visit and the subjects must complete the study. Subjects who do not have an analysis visit Week 4 mean NRS score assessing average pain intensity in the past 24 hours will be set to a non-responder.

- Responder at ≥50% Pain Reduction:
 - Subjects achieving ≥50% pain reduction on the mean NRS score assessing average pain intensity in the past 24 hours from baseline to Week 4 analysis visit and the subjects must complete the study. Subjects who do not have an analysis visit Week 4 mean NRS score assessing average pain intensity in the past 24 hours will be set to a non-responder.
- Responder at ≥30% Pain Reduction and Week 4 PGI-C Improved Score:
 - Subjects achieving ≥30% pain reduction on the mean NRS score assessing average pain intensity in the past 24 hours from baseline to Week 4 analysis visit and the subjects must complete the study. Subjects who do not have an analysis visit Week 4 mean NRS score assessing average pain intensity in the past 24 hours will be set to a non-responder.
 - o In addition, to be classified as "responders" subjects must have an analysis visit Week 4 PGI-C score of 1 (Very Much Improved) or 2 (Much Improved). Otherwise, those subjects will be set to non-responders.

The percent change from baseline that is \leq -30.0% is equivalent to \geq 30% pain reduction. Subjects with a calculated mean NRS score assessing average pain intensity in the past 24 hours at analysis visit Week 4 will be provided in a figure based on their percent change from baseline values. The horizontal axis displays a range of percentage-reductions from baseline at Week 4 in the mean NRS score assessing average pain intensity in the past 24 hours and the vertical axis displays the percentage of subjects achieving each of those levels of improvement. The horizontal axis will range from 0% to 100% in percentage-reductions and will not plot subjects with percentages below 0% (i.e. subjects that showed worse pain at Week 4 and the percentage change from baseline \geq 0%).

Frequency distributions, odds ratio, and relative risk analyses described in Section 5.3.5.5 will be used to summarize the responder status endpoints.

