9.3.4 Number of Days to Sustained Pain Reduction

If a subject reaches a responder status at any point of the study as defined in Section 9.3.3, the following additional conditions will also need to be met in order for the subject to be considered as sustaining pain reduction:

Protocol No.: NYX-2925-2001

- At least 8 days from the onset of the response to the last collected pain score that is \leq Study Day 28.
 - o Study Day 21 is the latest possible day for sustained pain reduction if the study day NRS score assessing average pain intensity in the past 24 hours was collected.
- The responder status endpoint of interest stated in Section 9.3.2 must by met at the Week 4 analysis visit.
 - Responder at ≥30% Pain Reduction
 - o Responder at ≥50% Pain Reduction
- Once the responder status has been met, the remainder of the study days after the last day in the 4-day interval until Study Day 28 will calculate the overall remaining mean for NRS score assessing average pain intensity in the past 24 hours. If the overall remaining mean score shows a pain reduction \geq to the responder status (i.e. \geq 30% or \geq 50%), then this criteria of the sustained pain reduction will be met.

A frequency distribution of these categories will be summarized:

- >30% Pain Reduction Status
 - Never Reached
 - o Reached, but did not Sustain
 - Reached and Sustained at Mean Analysis Visit Week 4 (Responder Endpoint)
- >50% Pain Reduction Status
 - Never Reached
 - o Reached, but did not Sustain
 - Reached and Sustained at Mean Analysis Visit Week 4 (Responder Endpoint)

The number of days of onset to sustained pain reduction will be summarized using descriptive statistics. The same Cox proportional hazards modeling analyses and Kaplan-Meier probability plot described in Section 9.3.3 will be applied to sustained pain reduction data. The number of days to sustained pain reduction will be based on the observed daily pain scores and will not use any imputation methods for missing data described in Section 9.1.3.

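### Time to sustained pain reduction: dropouts are non-events by definition but are censored when they leave, which raises that arm's Kaplan-Meier curve and Cox hazard ratio

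*SAP*

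**What the plan says.** **Censoring.** SAP 5.3.5.4 states that for a subject who never reaches the responder status "the number of days will be censored at Day 28 or the day of the last particular efficacy assessment", whichever comes first. For the KM plots, "The same censoring technique will be used as stated in the Cox proportional hazards model".

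**Carry-over.** SAP 9.3.4: "The same Cox proportional hazards modeling analyses and Kaplan-Meier probability plot described in Section 9.3.3 will be applied to sustained pain reduction data". It gives no separate rule for subjects who leave early.

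**Event definition.** SAP 9.3.4 has three conditions. One is that the responder endpoint of SAP 9.3.2 "must by met at the Week 4 analysis visit". SAP 9.3.2 defines that endpoint by the reduction "from baseline to Week 4 analysis visit and the subjects must complete the study". It adds that a subject without a Week 4 mean "score assessing average pain intensity in the past 24 hours will be set to a non-responder". The event is dated back to the first day of the qualifying 4-day interval (SAP 9.3.3), and SAP 9.3.4 gives Day 21 as the latest possible event day.

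**Protocol.** Section 12.5.2 censors subjects who miss the target at the end of their last week with pain scores, and includes sustained reduction in that rule.

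**The concern.** Censoring on Day 15 tells the Cox model and the KM estimator that the subject remained able to have the event, at the rate of those still in the study. Under SAP 9.3.2 and 9.3.4 that chance is zero. A subject who responded from Day 3 and left on Day 15 is a non-event because of leaving. No assumption about the unseen pain scores can alter this, so it differs from the usual debate about informative censoring.

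Removing known non-events from the risk set makes each later event count for more. The affected results are an adjusted HR, 95% interval and p-value for each dose against placebo, and a KM figure, at both the 30% and 50% thresholds. In a multi-dose phase 2 trial, an arm could look better on durability of response partly because it lost subjects early.

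**Working it through.** **1. Figures in the plan.** The only figure tied to this endpoint is the Day 21 limit, and it reproduces: 28 − 21 + 1 = 8 days, the minimum run that SAP 9.3.4 requires. SAP 4.4 supplies 75 subjects per arm. Its power statement concerns the primary t-test only (75 per group, difference 1.05, SD 2.25, two-sided 0.05) and reproduces at 81.0% against the stated 80%. No event count, dropout rate or sustained-response rate is given anywhere.

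**2. Assumptions.** Sustained proportion r = 30% in both arms, so the HR should be 1.00. Dropout fraction d is spread evenly over Days 3-18 (16 days). Onset of sustained response is either uniform over Days 1-21, or front-loaded with weights exp(−t/k), k = 4 to 7 days. Cox has treatment only, with no baseline covariate. Expected counts are used, so there is no simulation noise.

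**3. Formulas.** With e(t) events and c(t) censorings on day t, the risk set is R(t+1) = R(t) − e(t) − c(t), and the KM probability is 1 − Π[1 − e(t)/R(t)].

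**4. One arm by hand (d = 20%, uniform onset).**
- e(t) = 75 × 0.30 / 21 = 1.071 on Days 1-21.
- c(t) = 75 × 0.20 / 16 = 0.9375 on Days 3-18.
- SAP rule: R(21) = 75 − 20 × 1.071 − 15 = 38.57, so the Day 21 hazard is 1.071 / 38.57 = 2.8%.
- All non-events censored at Day 28: R(21) = 75 − 21.43 = 53.57, so the hazard is 2.0%.
- KM over all days: 34.2% under the SAP rule, 30.0% under Day 28 censoring.

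The ceiling, when all dropout precedes all events, is r/(1 − d) = 0.30/0.80 = 37.5%. The floor is r, reached when all dropout follows Day 21.

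**5. Two arms.**

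| Dropout, higher vs lower arm | Onset | KM, SAP rule | HR, SAP rule | KM and HR, Day 28 rule |
|---|---|---|---|---|
| 20% vs 8% | uniform | 34.2% vs 31.5% | 1.09 | 30.0% both, 1.00 |
| 20% vs 8% | front-loaded | 31.1-32.1% vs 30.4-30.8% | 1.02-1.04 | 30.0% both, 1.00 |
| 30% vs 10% | uniform | 37.2% vs 31.9% | 1.17 | 30.0% both, 1.00 |
| 30% vs 10% | front-loaded | 31.8-33.5% vs 30.5-31.0% | 1.04-1.08 | 30.0% both, 1.00 |
| 20% vs 20% | uniform | 34.2% both | 1.00 | 30.0% both, 1.00 |

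Swapping the arms inverts the HR: with 20% dropout on placebo and 8% on active, uniform onset, it is 1/1.093 = 0.915.

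**6. Dependence on timing.** With 5% placebo dropout, dropout confined to after Day 21 gives an HR of 1.00 in every case. The most extreme case tried (30% active dropout, all in Week 1, late onset) gives KM 42% and HR 1.42.

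**7. Against the trial's precision.** With 22.5 expected events per arm, the SE of log HR is √(1/22.5 + 1/22.5) = 0.298, so a 95% interval spans a factor of exp(1.96 × 0.298) = 1.8 each way. In a simulation at 75 per arm with uniform onset, two-sided rejection was 5.3% under the SAP rule and 4.5% under the Day 28 rule at 20% vs 8% dropout. At 30% vs 10% it was 9.1% and 5.0%.

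**The case against.** **The effect is small and the endpoint minor.** This is largely true. The endpoint is exploratory, its table and figure are not in the topline set, and nothing is adjusted for multiplicity. At moderate imbalance the shift is well inside the confidence interval. That limits the weight of the point but does not make the rule right.

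**Censoring may target response had nobody dropped out.** The SAP does not say so, and its event definition says the opposite. The rule does not deliver that quantity either. Suppose both arms would show 35% sustained response without dropout, and dropout is uniform at 20% vs 5%. The SAP rule then gives KM 30.6% vs 34.0% and HR 0.88, neither 35% nor 1.00. Dropouts whose response had already begun stay in the risk set past their onset as non-events.

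**Readings that go too far.**
- A reader might infer that the reported response rate is inflated. It is not. SAP 5.3.5.4 presents crude n (%) of responders and of censored subjects and uses KM for plots only. The frequency table in SAP 9.3.4 and the odds ratios and relative risks for the Week 4 responder endpoints in SAP 9.3.2 are also unaffected.
- A reader might say that the KM curve contradicts that frequency table. The two differ because a censored curve and a crude proportion answer different questions, and both are reported.
- A reader might expect the bias to favour the higher doses through adverse-event dropout. The documents do not support a direction. Protocol section 4 reports no adverse event leading to discontinuation in the multiple-dose phase 1 part (up to 900 mg for 7 days), and Protocol 7.4 lists lack of efficacy as a withdrawal reason, which could fall more heavily on placebo.
- A reader might treat all dropout as harmful. Dropout after Day 21 has no effect.

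**Conclusion.** The censoring rule does not fit the sustained-reduction endpoint. By SAP 9.3.2 and 9.3.4 a dropout is a known non-event, and SAP 5.3.5.4 treats that subject as still at risk until lost from view. Relative to the SAP's own definition, dropout before Day 21 raises that arm's KM curve and its HR. The HR need not exceed 1; it is higher than it would be under Day 28 censoring. With equal dropout only the KM curves are too high.

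Under the stated assumptions the HR is about 1.02-1.09 at 20% vs 8% dropout and 1.04-1.17 at 30% vs 10%, against 1.00. These sizes rest on assumed dropout, response and onset patterns. The direction rests on the SAP's rules alone and reverses against NYX-2925 if placebo loses more subjects. Time to first response (SAP 9.3.3) does not require completion and is not touched, nor is any primary or secondary result.

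**What to change.** Add one sentence to SAP 9.3.4: for sustained reduction only, every subject who does not achieve it, dropouts included, is censored at Day 28 in both the Cox model and the KM plot. The KM value at Day 21 then equals the crude sustained proportion. Keep the present rule for time to first response.

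Protocol 12.5.2 carries a similar rule for sustained reduction, so list the departure in SAP 4.7. Treating dropout as a competing event is an alternative. The present rule could be kept as a sensitivity analysis.

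Cost: one more documented departure from the protocol and a little programming. No new data are needed.

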5.4 Analysis Visits

Analysis visits are determined based on the collected/derived data for the study that will be used for listings and statistical analyses. In some events, there may be differences in visits depending on the data used for statistical summaries and as a result analysis visits are defined. For example, data for efficacy versus safety may have different methods for defining the analysis visits. The subsections below represent the analysis visits that will be used to support the analyses in this SAP.

In the event more than one record is collected/derived within an analysis visit, the non-missing record with the date closest to the target day will be selected. If there is a tie between two dates between the target date, then the first date will be used. Unless otherwise specified in Sections 9 and 10, if more than one non-missing record occurs on the same date, then the first planned scheduled result will be used.

Clinical laboratory tests will also consider lowest, highest, and most abnormal post-baseline results as additional analyses. More details are provided in Section 10.2.

5.4.1 Safety Analysis Visits

Each safety analyses section will state which analysis visits will be used in their respective summary tables. All collected/derived records will be included in the appendix listings.

Protocol and/or CRF Term	Analysis Visit (Target Day)	Study Day Window
Visit 1/Screening/Weeks -4 to -1	Screening (-28)	≤ Day -1
Visit 2/Baseline/Week 0	Day 1 (1)	Only Day 1
N/A	Baseline ^(a) (N/A)	≤ Day 1
N/A	Unscheduled Week 1 (N/A)	Day 2 to Day 9
Visit 3/Week 2	Week 2 (14)	Day 10 to Day 18
N/A	Week 2/ET ^(b) (14)	Day 10 to Day 18
N/A	Unscheduled Week 3 (N/A)	Day 19 to Day 23
Visit 4/Week 4	Week 4 (28)	Day 24 to Day 32
N/A	Week 4/ET ^(c) (28)	Day 24 to Day 32
Visit 4/Early Termination	Early Termination ^(b,c) (N/A)	Day 2 or Later
Visit 5/Week 5/Follow-Up	Follow-Up ^(d) (35)	Day 33 to Day 39
N/A	Repeat Follow-Up ^(e) (N/A)	Any Repeat Follow- Up Visits
N/A	Last Post-Baseline Visit ^(f) (N/A)	Day 2 or Later
N/A	Overall Post-Baseline Visits ^(g) (N/A)	Day 2 or Later

⁽a) Baseline definition described in Section 5.1.4.

⁽b) For listings, the Week 2/ET visit will be displayed if it can be mapped within the Day 10 to Day 18 study day window for Week 2 and there was not a scheduled Week 2 visit. Otherwise, Early

Termination will be displayed in the listing. For analysis purposes for displaying the analysis visits, Week 2/ET will be pooled with Week 2 data.

- (c) For listings, the Week 4/ET visit will be displayed if it can be mapped within the Day 24 to Day 32 study day window for Week 4 and there was not a scheduled Week 4 visit. Otherwise, Early Termination will be displayed in the listing. For analysis purposes for displaying the analysis visits, Week 4/ET will be pooled with Week 4 data.
- (d) Subjects will return to the study site 7 days following the Week 4/Early Termination visit to assess adverse events and concomitant medication use. The adverse event assessment will include any serious adverse events that were ongoing at the time of study completion, and whether any ongoing adverse events had progressed to becoming serious. Blood samples will be collected for liver function testing.
- (c) If subjects return after the Follow-Up visit for a repeat assessment, that visit and any additional visits will be identified as a Repeat Follow-Up visit.
- (f) This considers the last post-baseline values collected/derived for a particular set of data (including unscheduled and repeated measurements/assessments).
- (g) This is used for combining all post-baseline data. Examples of this are used for study drug accountability, compliance, treatment exposure, and rescue medication.

5.4.2 Efficacy NRS Pain Intensity Scores Analysis Visits

These analysis visits are for the daily diary data when the study-issued handheld devices where provided on Visit 1 (screening) until the devices are returned on the Week 4 or Early Termination visit.

Protocol and/or CRF Term	Analysis Visit	Study Day Window
Visit 1/Screening/Weeks -4 to -1	Screening ^(a)	≤ Day -8
Visit 1/Screening/Weeks -4 to -1	Baseline	Day -7 to Day -1
Visit 2/Baseline/Week 0	Week 1	Day 1 to Day 7
Visit 3/Week 2	Week 2	Day 8 to Day 14
N/A	Week 3	Day 15 to Day 21
Visit 4/Week 4	Week 4	Day 22 to Day 28
N/A	After Day 28 ^(b)	Day 29 or Later

⁽a) Screening values will be displayed in listings, but not included summary tables.

⁽b) Data collected after Day 28 will be displayed in listings, but not included summary tables with an analysis visit.

5.4.3 Efficacy DSIS Analysis Visits

Protocol No.: NYX-2925-2001

These analysis visits are for the daily diary data when the study-issued handheld devices where provided on Visit 1 (screening) until the devices are returned on the Week 4 or Early Termination visit.

Protocol and/or CRF Term	Analysis Visit	Study Day Window
Visit 1/Screening/Weeks -4 to -1	Screening ^(a)	≤ Day -7
Visit 1/Screening/Weeks -4 to -1 Visit 2/Baseline/Week 0	Baseline	Day -6 to Day 1
N/A	Week 1	Day 2 to Day 8
Visit 3/Week 2	Week 2	Day 9 to Day 15
N/A	Week 3	Day 16 to Day 22
Visit 4/Week 4	Week 4	Day 23 to Day 29
N/A	After Day 29 ^(b)	Day 30 or Later

⁽a) Screening values will be displayed in listings, but not included summary tables.

5.4.4 Other Efficacy Data Analysis Visits

Each efficacy analyses section will state which analysis visits that will be used in the summary tables. All collected/derived records will be included in the appendix listings.

Protocol and/or CRF Term	Analysis Visit (Target Day)	Study Day Window
Visit 1/Screening/Weeks -4 to -1	Screening (-28)	≤ Day -1
Visit 2/Baseline/Week 0	Day 1 (1)	Only Day 1
N/A	Baseline ^(a) (N/A)	≤ Day 1
N/A	Unscheduled Week 1 (N/A)	Day 2 to Day 10
Visit 3/Week 2	Week 2 (14)	Day 11 to Day 17
N/A	Week 2/ET ^(b) (14)	Day 11 to Day 17
N/A	Unscheduled Week 3 (N/A)	Day 18 to Day 24
Visit 4/Week 4	Week 4 (28)	Day 25 to Day 31
N/A	Week 4/ET ^(c) (28)	Day 25 to Day 31
Visit 4/Early Termination	Early Termination ^(b,c) (N/A)	Day 2 or Later
N/A	Last Post-Baseline Visit ^(d) (N/A)	Day 2 or Later

⁽a) Baseline definition described in Section 5.1.4.

^(b) Data collected after Day 29 will be displayed in listings, but not included summary tables with an analysis visit.

(b) For listings, the Week 2/ET visit will be displayed if it can be mapped within the Day 11 to Day 17 study day window for Week 2 and there was not a scheduled Week 2 visit. Otherwise, Early Termination will be displayed in the listing. For analysis purposes for displaying the analysis visits, Week 2/ET will be pooled with Week 2 data.

(c) For listings, the Week 4/ET visit will be displayed if it can be mapped within the Day 25 to Day 31 study day window for Week 4 and there was not a scheduled Week 4 visit. Otherwise, Early Termination will be displayed in the listing. For analysis purposes for displaying the analysis visits, Week 4/ET will be pooled with Week 4 data.

(d) This considers the last post-baseline values collected/derived for a particular set of data (included unscheduled and repeated measurements/assessments).

5.5 Data Imputations

Standard methods described below will be used for imputing missing data and character values in numeric collected parameter data.

5.5.1 Character Values in Numeric Data

Characters such as "<, >, and/or =" may be included in some parameter data values that are supposed to be collected in a numeric format. This is most commonly seen in laboratory data. Analysis values for results with "<=" or ">=" will be analyzed with those characters stripped from the collected result (i.e. "<=1.030" = "1.030" and ">=100" = "100").

Analysis values with only "<" will be handled using these methods:

- For precision data collected with at least one number after the decimal point, the analysis value will be the numeric value minus 1 extra precision unit (i.e. "<0.1" = "0.09").
- For whole numbers collected and the value reported as "<0" then the analysis value will be 0.
- For other whole numbers collected, the analysis value will be the numeric value minus 1.

Analysis values with only ">" will be handled using these methods:

- For precision data collected with at least one number after the decimal point, the analysis value will be the numeric value plus 1 extra precision unit (i.e. ">5.25" = "5.251").
- For whole numbers collected, the analysis value will be the numeric value plus 1.

Documentation of how to handle other unplanned characters found in the data for numeric parameter results will be described in the ADaM Analysis Data Reviewer's Guide.

For listing purposes, the collected results will be displayed in the CSR listings and appendices (i.e. "<5.0" over "4.99").

